## 9. STATISTICS

### 9.1. *Description of statistical methods*

Demographic and other baseline patient characteristics (age, gender, disease duration, prior and concomitant disease, prior and concomitant therapy) will be compared between therapy groups to demonstrate comparability between groups at baseline using appropriate statistical tests.

Descriptive statistics for data whose distribution follows the law of normal distribution will be presented using the arithmetic mean and standard deviation. For otherwise distributed data descriptive statistics will be presented using non-parametric measures (median/mod, quartiles).

Two-sided confidence intervals will be used to assess treatment efficacy (primary and secondary efficacy criteria).

For primary and secondary efficacy criteria, differences will be considered statistically significant at the p-value level of <0.05.

In accordance with the purpose of the trial, statistical analysis of the results is planned to compare the efficacy of the therapy regimen including Mexidol® in the treatment of attention deficit hyperactivity disorder (ADHD) in children 6-12 years old at different dosing regimens with the efficacy of the regimen including placebo and a combination of the Investigational product and placebo.

The main efficacy criterion is the mean change in the total score on the inattention and hyperactivity/impulsivity subscales of the SNAP-IV scale after 6 weeks of therapy vs. baseline. Descriptive statistics for this indicator will be given and the following statistical hypotheses will be tested:

$$H^0: \mu_p = \mu_T; \\ H^1: \mu_T < \mu_p$$

$\mu_T$  - mean change in SNAP score in the trial group (group 1 Mexidol®, 125 mg OD, or group 2 (Mexidol®, 125 mg BID);

$\mu_p$  - mean change in SNAP score in control group 3 (placebo). The sign " $<$ " is associated with the fact that the change has a negative value.

Comparison of the values of the two groups of patients will be performed by calculating the two-sided 95% confidence interval for the difference of  $\mu_1$  ( $\mu_2$ ) and  $\mu_0$  values. A conclusion on superiority can be made if the upper bound of the two-sided 95% confidence interval for the difference in mean changes in SNAP scores of Mexidol® vs. placebo is negative.

Testing of the null statistical hypothesis can be done using one-factor analysis of variance with Dunnett's posterior criterion and evaluation of contrasts or similar applicable statistical analysis method.

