To assess the variability of the effect, the coefficient of variation (CV) value was calculated for all the above change values in the active treatment group:

$$CV = \frac{SD}{M}$$

The following values are obtained:

- 114%
- 167%

of which the maximum of 167% was used to estimate the standard deviation, which for the selected value of change corresponds to the value of  $4.5 * 1.67 = 7.515$ .

For the placebo group, the actual data above were used (-2.0 and -4.7 for mean and standard deviation, respectively).

In order to calculate the sample size, the following assumptions were made:

1. One-sided hypothesis of superior efficacy of Mexidol® over placebo.
2. The mean change in SNAP score in the placebo group is -2.0 points, and the standard deviation for the change is 4.70 points.
3. The mean change in SNAP score in the Mexidol® group is -4.5 points, and the standard deviation for the change is 7.515 points.
4. The modulus of the difference in mean SNAP scores between the Mexidol and placebo groups is 2.5 points
5. The pooled variance estimate (pooled variance) is:

$$SE = \sqrt{\frac{CO_1^2 + CO_2^2}{2}} = \sqrt{\frac{0.12, 0.46}{2}} = 6.27$$

6. The minimum adequate strength is 80% (consequently, the II error is 0.20).
7. The ratio of group volumes is 1:1:1:1.
8. The significance level is 95% (respectively, the I error is 0.05). Since the boundaries of the 95% confidence interval must be two-sided and testing of the superiority hypothesis is one-sided, a one-sided error I of 0.025 will be applied to test the hypothesis, which is equivalent to an error of 0.05 for a two-sided test.
9. 20% drop-out rate during screening.
10. 10% drop out rate during follow-up (based on the above studies).

All calculations were based on the formulae from the book (page 228), where the approximating function for power is given by the following equation

$$1 - \beta = 1 - F(t_{K,\alpha} - \Delta)$$

$$\frac{\sigma\sqrt{2/n}}{\Delta}$$

Where  $\Delta$  - clinically acceptable minimal difference (difference) from placebo and  $Fz = \int_{-\infty}^{z_{\alpha/2}} \text{Normal}(0,1) dz$ , which can also be written by the following expression for n:

$$n = \frac{2\sigma^2 [t_{\alpha/2} + z_{\beta}]^2}{\Delta^2}$$

Calculations were performed using the statistical package PASS 11 (NCSS Inc., USA), which is a validated package that uses formulae directly from the book by Chow et al. cited above.

The results of the calculations are as follows:

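### If the deciding 95% intervals come from the ANOVA/Dunnett named in the plan, its three-arm pooled variance makes them about 7% too wide on the plan's own SDs and costs about 4 points of power per dose.

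*Protocol*

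**What the plan says.** **Decision rule.** Protocol 9.1 and SAP 7 declare a dose superior when the upper limit of the two-sided 95% interval for its difference from placebo, in mean SNAP-IV change, lies below zero. Neither says which variance estimate goes into that interval.

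**Test.** Both sections then say: "Testing of the null statistical hypothesis can be done using one-factor analysis of variance with Dunnett's posterior criterion and evaluation of contrasts". The sentence ends by allowing some similar applicable method.

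**Planning assumptions (Protocol 9.2, repeated in SAP 8).**
- Placebo: "The mean change in SNAP score in the placebo group is -2.0 points, and the standard deviation for the change is 4.70 points".
- Drug, with no distinction between doses: "The mean change in SNAP score in the Mexidol® group is -4.5 points, and the standard deviation for the change is 7.515 points".
- Difference: "The modulus of the difference in mean SNAP scores between the Mexidol and placebo groups is 2.5 points".
- Error rate: "a one-sided error I of 0.025 will be applied to test the hypothesis".
- The sample size uses 6.27, the root mean square of the two SDs, and arrives at 100 completers per arm for 80% power.

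**Templates.** SAP Table 3, for the primary endpoint, gives an independent-samples t-test or a Mann-Whitney test for the comparison of drugs, chosen by the shape of the distribution. Neither document names a Welch or other unequal-variance method, or a check of equal variances.

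**The concern.** A contrast inside a one-factor ANOVA takes its standard error from all arms, including the one not being compared. Equal arm sizes give a two-sample t interval the right standard error when the two SDs differ. They do not do so for a contrast within a three-arm model. The pooled standard error is too large when the third arm varies more than the average of the two arms compared, and too small when it varies less.

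The plan assumes that the change on drug has 2.6 times the variance of the change on placebo (7.515²/4.70² = 56.48/22.09). For either dose against placebo, the third arm is then the other, more variable dose, so the pooled standard error is too large. Superiority is read from the upper limit of the interval, so excess width lowers the chance of showing an effect of the planned size. The sample size was set with a two-arm SD of 6.27, which is not the SD that this ANOVA would use.

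**Working it through.** **Inputs.** SD 4.70 on placebo, 7.515 on each dose, difference 2.5, one-sided 0.025, 100 completers per arm (Protocol 9.2, SAP 8).

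**1. The plan's own figure.** Two-arm SD = √((22.09 + 56.48)/2) = 6.27. The normal formula gives 99 per arm. With the t distribution, power is 79.8% at 99 and 80.2% at 100. The stated 100 reproduces.

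**2. Standard error for one dose against placebo.**
- True: √((22.09 + 56.48)/100) = 0.886.
- ANOVA: residual SD = √((22.09 + 2 × 56.48)/3) = 6.71, so SE = 6.71 × √(2/100) = 0.949.
- Ratio: 0.949/0.886 = 1.070.

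**3. 95% half-widths.**
- ANOVA (297 df): 1.968 × 0.949 = 1.87.
- Welch (166 df): 1.974 × 0.886 = 1.75.
- Two-sample Student (198 df): 1.972 × 0.886 = 1.75, which is practically the Welch width.

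**4. Error and power without a multiplicity adjustment.** The standardised effect is 2.5/0.886 = 2.820.
- ANOVA: effective critical value 1.968 × 1.070 = 2.107. One-sided error = Φ(−2.107) = 1.8%. Power = Φ(2.820 − 2.107) = 76.2%.
- Welch: power = Φ(2.820 − 1.974) = 80.1%.
- Simulation with normal data agrees: coverage 96.4% and power 76% for ANOVA, 95.0% and 80% for Welch.
- About 110 completers per arm would bring the ANOVA contrast back to 80%.

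**5. With Dunnett (critical value 2.22).**
- Pooled variance: Φ(2.820 − 2.22 × 1.070) = 67%.
- The two arms' own variances, same critical value: Φ(2.820 − 2.22) = 73%.
- The usual value assumes a correlation of 0.5 between the two comparisons. On the plan's SDs it is 22.09/(22.09 + 56.48) = 0.28. Keeping the one-sided value of 2.21 with separate variances gives a familywise error of about 2.7% instead of 2.5%.
- At correlation 0.28 the large-sample value is about 2.23, and power is Φ(2.820 − 2.23) = 72%. The gain over pooling is therefore 4 to 5 points.

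**6. Sensitivity to the SD assumption (same SD on both doses).**

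| Drug SD / placebo SD | ANOVA width against correct width |
|---|---|
| 0.8 | 4% too narrow (coverage about 94%) |
| 1.0 | equal |
| 1.2 | 3% too wide |
| 1.4 | 5% too wide |
| 1.6 (the plan) | 7% too wide |

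**7. A case outside the plan: one dose at 7.515, the other at 4.70 like placebo.** Residual SD = √((2 × 22.09 + 56.48)/3) = 5.79, so the ANOVA SE is 0.819.
- Wide-spread dose: true SE 0.886. Simulated coverage is 93% and one-sided error 3.5% without adjustment.
- Other dose: true SE √(2 × 22.09/100) = 0.665, so the interval is 23% too wide (coverage 98.4%, error 0.8%).
- With Dunnett at 2.21 the errors are 2.1% and 0.3%, and the familywise error is 2.4%.

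**The case against.** **The interval is not tied to the ANOVA.** The wording is permissive, the interval is described in a separate sentence as a comparison of two groups, and SAP Table 3 names a two-sample test. On the t-test route, at equal arm sizes, there is practically no width error. This stands, and it is why the point is conditional. It does not remove the point: ANOVA with Dunnett is the only test of the primary hypothesis named in the running text, no passage settles which method gives the deciding interval, and the alternative in Table 3, Mann-Whitney, gives no interval for a difference in means.

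**The SDs are planning devices.** The placebo SD comes from one published trial. The drug SD is 4.5 × 1.67, using the larger of two coefficients of variation from trials of other ADHD treatments. This also stands: at a smaller SD ratio the excess width shrinks, and at equal SDs it vanishes.

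**A stronger reading is tempting.** A reader might infer that the deciding intervals are invalid and that false claims of superiority become more likely. The documents do not support that. On the plan's assumptions the error is below nominal. A too-narrow dose-versus-placebo interval needs either two doses with different spread or a placebo arm more variable than the drug arms, and the plan assumes neither. In the unequal-dose case above, Dunnett still keeps the familywise error near 2.4%; it is only split unevenly between the doses.

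**One contrast would be too narrow on the plan's SDs: dose against dose.** Its pooled SE of 0.949 compares with a true √(2 × 56.48/100) = 1.063, for coverage of about 92%. The SAP Table 6 template has a column for it, but it is not among the stated primary hypotheses, so no claim against placebo rests on it.

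**Conclusion.** The point holds in conditional form. If the dose-versus-placebo intervals are taken from the ANOVA/Dunnett named in Protocol 9.1 and SAP 7, they are about 7% too wide on the plan's own inputs. About 4 points of power per dose are lost without adjustment, and 4 to 5 with Dunnett. This rests on 100 completers per arm, SDs of 4.70 and 7.515, the same SD on both doses and roughly normal changes. It is a modest loss of precision and power and a gap in specification, not a failure of error control. It is worth correcting because the remedy costs almost nothing and also settles which variance the deciding interval uses.

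**What to change.** In Protocol 9.1 and SAP 7, state that each dose-versus-placebo difference and its 95% interval use the variances of those two arms, by a Welch interval or a linear model with group-specific variances. Change the footnote to the SAP Table 3 template so that it names the same method; otherwise the text and the template would still disagree.

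If a Dunnett-type adjustment is kept, apply it to those standard errors and compute the critical value from the resulting correlation (about 0.28 on the plan's SDs), not from the equal-variance table.

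The cost is a few sentences and one model option in R, which SAP 9 already names. No patients or new data are needed. If the SDs turn out equal, the loss is a few degrees of freedom, about 0.1 to 0.2 points of power. The choice should be fixed before unblinding.

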## **9.2. Planned number of patients**

To justify the sample size, a search was conducted for publications on the efficacy of treatments for children and adolescents with ADHD that evaluated efficacy using the SNAP scale.

Among studies conducted on a similar population with similar endpoints, Dell'Agnello G, Maschietto D, Bravaccio C, Calamoneri F, Masi G, Curatolo P, Besana D, Mancini F, Rossi A, Poole L, Escobar R, Zuddas A was detected; LYCY Trial Group. Atomoxetine hydrochloride in the treatment of children and adolescents with attention-deficit/hyperactivity disorder and comorbid oppositional defiant disorder: A placebo-controlled Italian trial. Eur Neuropsychopharmacol. 2009 Nov;19(11):822-34, in which the change in the sum of scores on the "inattention" + "hyperactivity/impulsivity" domains of the SNAP-IV scale was evaluated as the primary endpoint - this trial was used to estimate the magnitude of effect in the placebo group. According to the data published in the above trial, the change in score in the placebo group was -2.0 (4.7).

Since no studies of Mexidol® for the indication under study have been conducted previously, the data of the above-mentioned trial and the trial by Shang CY et al were used for approximate estimation of the effect size.

Based on the data from the two studies cited, a similar SNAP rate would be expected at an average level across the two studies:

- Change -8.1 (9.2), n=105; 95% CI: -9.88 to -6.32 (minimum value -6.32).
- Change, 3.33 (5.58), n=75; 95% CI: -4.64 to -2.02 (minimum value, 2.02).

95% confidence intervals were calculated based on the following formulae:

$$\text{SEM} = \frac{\text{SD}}{\sqrt{n}}$$

$$\text{DI} = M \pm t_{\alpha, n-1} \times \text{SEM}$$

where: SEM - standard error of the mean;

SD - standard deviation;

n - number of observations;

CI - confidence interval;

M - mean.

Using the minimum values (lower limits of the confidence interval), the weighted average was calculated using the following formula:

$$m = \frac{-6.32 \times 105 - 2.02 \times 75}{105 + 75} = -4.5283$$

For further calculations, -4.5 scores rounded to tenths were used.

Although this estimate is based on experience with another ADHD medication, it suggests minimal clinically significant differences and can be used to justify the sample size for Mexidol®.

To assess the variability of the effect, the coefficient of variation (CV) value was calculated for all the above change values in the active treatment group:

$$CV = \frac{SD}{M}$$

The following values are obtained:

- 114%
- 167%

of which the maximum of 167% was used to estimate the standard deviation, which for the selected value of change corresponds to the value of  $4.5 * 1.67 = 7.515$ .

For the placebo group, the actual data above were used (-2.0 and -4.7 for mean and standard deviation, respectively).

In order to calculate the sample size, the following assumptions were made:

1. One-sided hypothesis of superior efficacy of Mexidol® over placebo.
2. The mean change in SNAP score in the placebo group is -2.0 points, and the standard deviation for the change is 4.70 points.
3. The mean change in SNAP score in the Mexidol® group is -4.5 points, and the standard deviation for the change is 7.515 points.
4. The modulus of the difference in mean SNAP scores between the Mexidol and placebo groups is 2.5 points
5. The pooled variance estimate (pooled variance) is:

$$SE = \sqrt{\frac{CO_1^2 + CO_2^2}{2}} = \sqrt{\frac{0.12, 0.46}{2}} = 6.27$$

6. The minimum adequate strength is 80% (consequently, the II error is 0.20).
7. The ratio of group volumes is 1:1:1:1.
8. The significance level is 95% (respectively, the I error is 0.05). Since the boundaries of the 95% confidence interval must be two-sided and testing of the superiority hypothesis is one-sided, a one-sided error I of 0.025 will be applied to test the hypothesis, which is equivalent to an error of 0.05 for a two-sided test.
9. 20% drop-out rate during screening.
10. 10% drop out rate during follow-up (based on the above studies).

All calculations were based on the formulae from the book (page 228), where the approximating function for power is given by the following equation

$$1 - \beta = 1 - F(t_{K,\alpha} - \Delta)$$

$$\frac{\sigma\sqrt{2/n}}{\Delta}$$

Where  $\Delta$  - clinically acceptable minimal difference (difference) from placebo and  $Fz = \int_{-\infty}^{z_{\alpha/2}} \text{Normal}(0,1) dz$ , which can also be written by the following expression for n:

$$n = \frac{2\sigma^2 [t_{\alpha/2} + z_{\beta}]^2}{\Delta^2}$$

Calculations were performed using the statistical package PASS 11 (NCSS Inc., USA), which is a validated package that uses formulae directly from the book by Chow et al. cited above.

The results of the calculations are as follows:

- number of patients to complete the trial according to the protocol = at least 100 in each group or a total of at least 300;
- number of randomized patients = 111 in each group or a total of 333;
- number of patients screened, taking into account expected drop-out rate at screening of  $\approx 20\% = 417$ .

### **9.3. *Applied significance level***

The plan is to apply a significance level of 0.05 and calculate a two-sided 95% confidence interval.

### **9.4. *Criteria for trial termination***

The trial does not include interim data analyses and statistical criteria for trial termination.

### **9.5. *Procedures for recording missing, unanalysable and questionable data***

Missing, unanalysable and questionable data will not be replaced and taken into account in the statistical analysis of results.

### **9.6. *Procedures for reporting any deviations from the original statistical plan***

The details of the statistical analysis will be presented in the statistical analysis plan. The statistical analysis plan will be approved before the database cut off. All deviations from the approved version of the statistical analysis plan will be justified in the clinical trial report.

### **9.7. *Selection of data for statistical analysis***

Analyses will be conducted in the following populations:

- 1) safety population - will include all randomized patients who have taken at least one dose of the Investigational product;
- 2) the full analysis set (FAS) population will include all randomised patients who have taken at least one dose of Investigational product and who have an assessment of response to therapy after 6 weeks of therapy. This will be the main population for efficacy analyses;
- 3) PP (per protocol population) is a subgroup of the FAS population that will include patients in the absence of significant protocol deviations with respect to inclusion/exclusion criteria, adherence to therapy, and use of concomitant therapy. This will be an additional population used for efficacy analyses.

## **10. DIRECT ACCESS TO SOURCE DATA/DOCUMENTATION**

It is the responsibility of the investigator to provide direct access to the source data/documentation to the employees of RPC PHARMASOFT LLC and its representatives, employees of authorized bodies for the purposes of monitoring, audit, expertise, and inspection. The Sponsor / Sponsor's representative must ensure that one of the patient's parents has given written consent for direct access to the patient's original medical records for the purposes of monitoring, auditing, ethical review, and inspection by authorized bodies.

### ***10.1. Protocol compliance***

The investigator conducts the clinical trial in accordance with a protocol developed by the Sponsor and approved by the appropriate regulatory authorities/independent ethical committee. Changes to the protocol are not permitted unless there is an immediate threat to trial subjects and if the changes relate to organizational and financial matters. The Sponsor must submit all protocol changes to the regulatory authorities/independent ethics committee as required. Any deviation from the protocol during its execution must be recorded and reflected in the trial documentation.

### ***10.2. Deviations from protocol***

In general, any deviation from the protocol may be accepted only in an urgent case or after obtaining written agreement from the Sponsor and subject to approval by the Ethics Committee. Any deviation from the protocol should be clearly explained in the source documentation and in the eCRF. Classification of protocol deviations will be made before the database cutt off by the Sponsor's medical expert. Deviations from the protocol will be considered significant in the following cases (the list may be expanded in a subsequent evaluation of protocol deviations):

- skip of visit 5;
- violation of inclusion / non-inclusion criteria;
- violation of the exclusion criteria;
- taking the Investigational product/placebo <80% or >120% of the total number of tablets prescribed;
- administration of prohibited drugs.

If significant deviations from the protocol are identified, the CRA must immediately inform the Sponsor.

In the absence of data at Visit 5 when data are available at Visit 6, these patients will not be included in the FAS and PP populations, but will be analysed in the safety population.

In the presence of data at Visit 5 and the presence of the other listed significant protocol deviations, these patients will be included in the full analysis population, safety population, but excluded from the protocol population.

### ***10.3. Confidentiality of patient data***

The investigator will ensure that the confidentiality of patient data is maintained. In the eCRF and any other documents submitted to the Sponsor, patients will be referred to by assigned numbers (codes) rather than by their names. Initials will not be used in this process. Documents not intended to be sent to the Sponsor, such as a list of personal data and associated patient identification numbers, must be kept strictly confidential by the investigator.

## **11. QUALITY CONTROL AND QUALITY ASSURANCE**

### ***11.1. Selection of Investigational sites***

The selection of investigational sites will be approved by the Sponsor prior to start of the trial to ensure that the personnel required in the trial are available and to assess the ability of these personnel to perform the trial in accordance with Good Clinical Practice requirements.

### ***11.2. Trial conduction***

All aspects of the clinical trial protocol must be adhered to during the clinical trial. If changes are necessary, they should be discussed without delay by the Investigator, CRA and Sponsor. Amendments to the clinical trial protocol must be made in writing and include a detailed justification for the changes. Amendments must be submitted to the Ministry of Health (MOH) and, once authorised by the MOH, to the LEC.

Each deviation from the trial protocol must be documented and justified by the investigator (or person designated by the investigator) in the appropriate place in the eCRFs and Investigator Site Files.

All other persons involved in the clinical trial process will be instructed by the investigator or CRA as to their tasks. This is the responsibility of the investigator.

